9.7.6.6 Patient Benefit Index (PBI-P)

The PBI-P questionnaire assesses the importance of treatment objectives to the individual. Before and at the end of drug treatment in this study, the patient completes the same questionnaire and rates the extent to which the treatment objectives have been achieved. The instrument consists of 27 multiple choice questions that can be answered “not at all”, “somewhat”, “moderately”, “quite” and “very”. The instrument can be found in [Appendix 4](#).

9.7.6.7 Prurigo Activity Score (PAS)

The PAS consists of 7 quantitative and qualitative measurements related to the examination of the skin. Type, number, distribution, affected body parts, and quantitative number of lesions in a representative body part are documented. The biggest lesion and the most representative lesion are monitored with documentation of height and area measurements. Prurigo lesion activity is recorded as a percentages based on their stage (0-4). Photographs of the body are conducted with monitored lesions marked. The instrument can be found in [Appendix 4](#).

9.7.6.8 Exploratory Histological Endpoints (at selected sites)

Punch biopsy skin material for measurement of nerve fiber density (histology) and MOR/KOR density (histology, Western Blot) analysis was obtained during TR03 (at selected sites). Punch biopsy will be obtained (at selected sites) during TV 14 for a comparative analysis with the results of the histological results of pre-dosing TR03 and end of study TR03 results.

9.7.6.8.1 MOR/KOR density and Nerve Fiber Density

The potential of nalbuphine HCl ER tablets to impact on the Measurement of nerve fiber density (histology) and MOR/KOR density (histology, Western Blot) in skin biopsies taken at Baseline visit and the Evaluation visit will be investigated at selected sites.

In addition to skin biopsy tissue obtained prior to drug treatment for H&E and analysis by a central reading dermatopathologist, at selected sites additional skin biopsy material obtained before and at the end of drug treatment will be compared to investigate, in an exploratory manner, any evidence of change in expression of MOR and KOR and nerve fiber density in relation to any noted changes in clinical study endpoints.

Bigliardi et al (2007) reports that in normal skin, keratinocytes express high amounts of MOR and it is therefore concluded that endogenous ligands are bound primarily to opioid receptors on keratinocytes and thus the endogenous opiate ligands are not binding to opioid receptors located on nerve endings –the net result is at most a weak itch signal to the central nervous system in the normal state. In chronic pruritic skin disorders, most opioid receptors on keratinocytes are reported as internalized; therefore there are many opioid ligands available to bind to opioid receptors on sensory nerve endings. This state leads, together with the changed morphology of the epidermal nerve endings, to a strong itch signal to the CNS. The authors reported that topical administration of the opioid mu receptor antagonist naltrexone in subjects with atopic dermatitis, lichen simplex chronicus or prurigo simplex showed an antipruritic effect. In addition, there was also an upregulation of epidermal MOR expression following two weeks of treatment, but no MOR upregulation in subjects who did not experience an antipruritic response. Bigliardi and Bigliardi-Qi (2004) reported that in PN human skin tissue samples there was a down regulation of the mu-opiate receptor (MOR) expression in the epidermis compared to normal skin.

Bigliardi-Qi et al (2009) reports that while it is widely accepted that KOR signaling

suppresses itch, there is currently no animal, behavioral or human data relating the regulation of skin KOR expression to pruritus. Salemi et al 2007 however reported high upregulation of KOR in the skin of fibromyalgia subjects that was thought to correlate with reported complaints of pain symptoms.

With regard to peripheral sensory nerve fiber density in the skin, Bigliardi et al (2009, 2007) report that epidermal nerve endings of pruritic skin in prurigo are thinner when compared to normal skin. In addition, the nerve fibers have a different morphology which may relate to initiating the sensation of pruritus because of the altered anatomical relationship to the various cellular elements of the skin.

9.7.7 Safety Assessments

Safety will be determined by evaluation of the following:

- AEs
- Vital signs including weight, BP, heart rate (HR), respiratory rate (RR), and body temperature
- Physical examination
- Clinical laboratory data (see [Appendix 3](#) for list of analytes)
- 12 Lead-ECG.

10 STUDY DRUG

Please see the Study Reference Manual for additional information on Study Drug supplies, packaging, storage, dispensation, and accountability.

10.1 FORMULATION, PACKAGING AND LABELING

The Study Drug in this trial is nalbuphine HCl ER tablets. Nalbuphine HCl ER tablets are white to off white film-coated round tablet containing either 30 mg or 60 mg nalbuphine HCl.

All study medication will be supplied by the Sponsor. Following confirmation of eligibility to start the Treatment Period, the patient will receive bottles of study drug tablets containing 60 tablets each. Bottles will be labeled with at minimum: contents, storage conditions, expiration date, clinical trial statement, and the name and lot number of the study drug Sponsor (Trevi Therapeutics).

10.2 SHIPPING, STORAGE AND HANDLING

The Investigator will ensure that the Study Drug is stored and dispensed in accordance with FDA and EU regulations concerning the storage and administration of investigational drugs. Nalbuphine HCl ER tablets should be stored at 20°C-25°C (68°F-77°F) with excursions permitted between 15°C and 30°C (59° to 86°F). The Study Drug should be stored away from any extreme conditions of temperature, light, or excess humidity.

10.3 UNBLINDING

Not applicable. This is an open-label study.

10.4 DRUG ACCOUNTABILITY

The Investigator must ensure that all drug supplies are kept in a secure locked area with access limited to those authorized by the Investigator. The Investigator must maintain accurate records of the receipt of all Study Drug shipped by the sponsor or the sponsor's representative, including but not limited to the date received, lot number, expiration date, amount received, and the disposition of all Study Drug. Current dispensing records will also be maintained including the date and amount of drug dispensed and the patient receiving the drug. All remaining drug not required by regulations to be held by the clinical facility will be destroyed on site at the end of the study.

11 PREMATURE DISCONTINUATION OF STUDY DRUG TREATMENT

Patients who complete Study Drug treatment through Treatment Visit 14 (even if some doses have been missed or if the patient was followed in the Observation Period before receiving study drug treatment) are considered to have completed Study Drug treatment. Patients discontinuing Study Drug treatment prior to Treatment Visit 14 will be considered to have prematurely discontinued Study Drug treatment. Patients removed from the study after enrollment and who have received a dose of study drug will not be replaced.

Some reasons for premature discontinuation of Study Drug treatment include:

- Withdrawal of consent to continue Study Drug treatment
- Intercurrent Illness
- Any intolerable AE that cannot be ameliorated or safely managed with medical intervention or one that poses undue risk to the subject if Study Drug treatment were continued in the opinion of the Medical Monitor or Investigator.

12 PREMATURE WITHDRAWAL OF PATIENTS FROM THE STUDY

Patients who complete study visits through the Evaluation visit of Week 10, even if there have been intervening missed visits, are considered to have completed the study.

All patients who receive study treatment should remain in the study whenever possible.

Reasons for withdrawal of the patient from the study include:

- Withdrawal of consent for study participation
- Premature discontinuation of Study Drug treatment
- Sponsor terminates the study for any reason
- Investigator decision

The Investigator may withdraw any patient from the study if, in the Investigator's opinion, it is not in the patient's best interest to continue on the study.

- Death of the patient
- Change in eligibility to participate in the study.

Any patient whose condition significantly changes after entering the study should be carefully evaluated by the Investigator and discussed with the Medical Monitor. Such patients should be withdrawn from the study if continuing would place them at risk or compromise the results of the study.

Patients who prematurely discontinue from the study will be asked to undergo and have completed all evaluations that may be necessary to ensure that the patient is free of untoward effects and to seek appropriate follow-up for any continuing problems. The date on which the patient is withdrawn from the study and the reason for discontinuation will be recorded on the CRF. When a patient is withdrawn prematurely from the study, (regardless of the reason), all evaluations required at the Early Termination visit will be performed. Patients who withdraw from the study will not be replaced.

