5 STUDY ENDPOINTS

5.1 PRIMARY ENDPOINT

- A description of the incidence and nature of TEAEs during Treatment Weeks 5-50

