- instruct patients to self-administer the first dose on the evening of Visit 1a at home
- instruct patients to notify the Investigator if any significant CNS AEs occur, and not to drive or operate dangerous machinery until the effect of the Study Drug can be assessed by the Investigator, see [Section 9.3](#)
- instruct the patient to take the Study Drug twice daily at approximately the same times of day and how to escalate from 30mg to 60mg BID.
- instruct patients to bring all remaining Study Drug to the Investigator site for each study visit.

For patients starting the Treatment Period, the next visit will be TV2.

For patients not qualifying for drug Treatment Period only (Visit 1a is also study visit OV1), the patient will enter the Observation Period and the next visit will be OV2.

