9.6.2.2.1 Treatment Visits 3-7 (TV3-TV7, Treatment Period Weeks 5-21)

The following procedures are to take place at these visits:

- obtain vital signs
- collect urine for pregnancy test (must be confirmed negative prior to dispensing study drug)
- collect blood for PK
- administer PRO measurements:
 - Worst itch NRS
 - Average daily itch intensity NRS
 - VRS
 - ItchyQoL
 - MOS Sleep-R
 - HADS

The PRO questionnaires must be administered at the study site under supervision by trained study staff, strictly adhering to PRO Administration Instructions (see Study Reference Manual).

- record AEs
- review of concomitant medications, including over-the-counter medications, nutritional supplements, and vitamins
- reinforce compliance
- perform study drug accountability, retrieve previously dispensed Study Drug
- Dispense the study drug to the patient required until next TV

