9.6.5.3 Visit 1b

See [Table 4](#) for summary of Visit 1b procedures.

Patients evaluated at OV 2-4 who record worst itch NRS>2 and are otherwise eligible can immediately begin Visit 1b. This patient then transitions into the Treatment Period and will undergo the following procedures:

- obtain vital signs
- conduct a physical examination
- collect central laboratory samples (hematology and chemistry)

- collect serum pregnancy sample in women of childbearing potential (done at the central laboratory)*
- collect urine for central lab urinalysis
- urine for pregnancy (must be confirmed negative prior to dispensing study drug)*

* If the urine pregnancy test result is negative and the serum pregnancy test result is positive, the patient is to be contacted and the following actions are to take place:

- instruct the patient to discontinue taking study drug
- schedule the patient for an unscheduled visit to collect another serum pregnancy test

The serum pregnancy test result will be used to determine the patient's eligibility to continue receiving study treatment. See [section 17.5.2.1](#) regarding how pregnancies are to be handled in this study.

- obtain blood for PK
- obtain a 12-lead ECG
- administer PRO measurements:
 - Worst itch NRS
 - Average daily itch intensity NRS
 - VRS
 - ItchyQoL
 - MOS Sleep-R
 - HADS
 - PBI-P

The PRO questionnaires must be administered at the study site under supervision by trained study staff, strictly adhering to PRO Administration Instructions (see Study Reference Manual).

- record AEs
- review of concomitant medications, including over-the-counter medications, nutritional supplements, and vitamins
- complete the PAS
- dispense Study Drug to the patient required until return at TV2
- instruct patients to self-administer the first dose on the evening of Visit 1b at home
- instruct patients to notify the Investigator if any significant CNS AEs occur, and not to drive or operate dangerous machinery until the effect of the Study Drug can be assessed by the Investigator, see [Section 9.3](#)
- instruct the patient to take the Study Drug twice daily at approximately the same times of day
- instruct patients to bring all remaining Study Drug to the Investigator site for each study visit.

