17.5.1 Adverse Event Definition

An AE is defined as any untoward medical occurrence in a clinical investigation patient reported on or after the first screening date. A treatment-emergent AE (TEAE) is any untoward medical occurrence in a clinical investigation patient or patient administered a pharmaceutical product on or after the initial administration of study medication on the evening of Visit 7. An AE does not necessarily have to have a causal relationship with the treatment. An AE can therefore be any unfavorable and unintended sign (including an

abnormal laboratory finding), symptom whether or not related to the medicinal (investigational) product, or disease temporally associated with the use of a medicinal (investigational) product.

The AE may be any of the following:

- a new illness
- worsening of a pre-existing condition
- worsening of a sign or symptom of the condition under treatment or of a concomitant illness
- an effect of the study medication, including comparator
- a combination of 2 or more of these factors.

No causal relationship with the study medication or with the clinical study itself is implied by the use of the term “AE.”

Surgical procedures themselves are not AEs; they are therapeutic measures for conditions that require surgery. The condition for which the surgery is required may be an AE. Planned surgical measures permitted by the clinical study protocol and the condition(s) leading to these measures are not AEs.

Adverse events fall into the categories “non-serious” and “serious.”

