19.9.2 Adverse Events

All treatment emergent AEs will be summarized overall and for each body system and preferred term by treatment group, relationship to study medication, and severity. For tabulations by severity, only a patient's most severe event within the category (e.g., overall, body system, or preferred term) will be counted. Adverse events will be dichotomized into "related" (probably and possibly) and "unrelated" (unlikely). "Treatment-emergent" will be defined as starting or worsening after the first dose of study medication. If the start date is missing, the event is assumed to be treatment emergent. All SAEs will be tabulated as well.

Although nalbuphine is not a controlled substance in the United States, adverse events of special interest that suggest a possible addiction or abuse potential or withdrawal will be specifically analyzed to screen for these effects. The list of MedDRA preferred terms for adverse events of special interest will be described in the Statistical Analysis Plan.

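### Section 12 of Version 1.0 defines study completion by a Week 10 Evaluation visit that this 50-week study does not have, so a literal reading overstates completion

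*Protocol*

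**What the plan says.** All of this is from Version 1.0.

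- **Study completion (Section 12).** The rule for counting a patient as a study completer begins: "Patients who complete study visits through the Evaluation visit of Week 10, even if there have been intervening missed visits, are considered". The same section lists premature discontinuation of study drug among the reasons for withdrawal from the study, and has the date and reason for withdrawal recorded on the CRF.
- **Treatment completion (Section 11).** Treatment is complete when the patient has been treated through TV14. "Patients discontinuing Study Drug treatment prior to Treatment Visit 14 will be considered to have prematurely discontinued Study Drug treatment".
- **Duration (Section 7 and Table 2).** Up to 50 weeks on drug, then a 2-week washout, for a total of up to 52 weeks.
- **Treatment emergence.** Section 17.5.1 counts events "on or after the initial administration of study medication on the evening of Visit 7". Section 19.9.2 says that treatment-emergent "will be defined as starting or worsening after the first dose of study medication", with no visit number. The visit instructions place the first dose elsewhere: "instruct patients to self-administer the first dose on the evening of Visit 1a at home" (Section 9.6.1) and "instruct patients to self-administer the first dose on the evening of Visit 1b at home" (Section 9.6.5.3).
- **Primary endpoint (Section 5.1).** "A description of the incidence and nature of TEAEs during Treatment Weeks 5-50".

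**The concern.** A completer rule has to name a visit that every treated patient can reach, and it should not be met before treatment is due to end. The Section 12 rule fails on both counts, and nothing else in the supplied text defines study completion correctly. Patient disposition is a planned summary (Section 19.4), and the frequency of and reasons for treatment discontinuation are a secondary endpoint (Section 5.2). In an open-label, long-term safety study, the proportion who complete is one of the figures a reader uses to judge tolerability. If sites or programmers apply Section 12 as written, patients who leave at any time between Week 10 and Week 50 are tabulated as completers.

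The Visit 7 wording in Section 17.5.1 is the same type of fault: a visit label that does not fit this schedule. It stands in the definition on which the primary endpoint depends, so it should be corrected too, but its consequences are smaller.

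**Working it through.** The plan states no figure for completion, so there is none to reproduce. The check sets each rule against the schedule.

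**1. Is there a Week 10 visit?** From Tables 3, 5 and 6, a direct entrant has TV1 to TV14 at Treatment Weeks 1, 3, 5, 9, 13, 17, 21, 26, 30, 34, 38, 42, 46 and 50, telephone contacts at Weeks 2 and 4, and the washout visit at Week 52. Week 10 is not among them; it falls between TV4 (Week 9) and TV5 (Week 13).

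In Table 8, TV2 comes two weeks after Visit 1b:
- OV2 entrants: 4 + 2 = Study Week 6
- OV3 entrants: 8 + 2 = Study Week 10
- OV4 entrants: 12 + 2 = Study Week 14

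So TV2 for OV3 entrants is the only visit at Study Week 10. With Visit 1b in Study Week 8 as Treatment Week 1, Study Week 10 is Treatment Week 10 − 8 + 1 = 3, which agrees with Table 5. This is the titration phase.

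**2. Is there an Evaluation visit?** No schedule table contains one. The term also appears in the biopsy text of Section 9.7.6.8.1, again without a place in the schedule.

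**3. How much of the study lies beyond the rule?** For a direct entrant, 50 − 10 = 40 treatment weeks remain, and 40/50 = 80%. The visits still to come are TV5 to TV14, which is 10 of 14. If a site took the nearest real visit instead, 50 − 9 = 41 weeks would remain after TV4 (82%) or 50 − 13 = 37 after TV5 (74%).

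**4. The rules side by side.** Take a direct entrant who stops drug and leaves at Week 20:
- Section 11: premature discontinuation of treatment, because it is before TV14.
- Section 12, list of reasons: withdrawn from the study.
- Section 12, opening sentence: completed the study.

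The last two cannot both hold.

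**5. Illustrative size.** The documents give no expected retention, so these figures are assumptions only. If drop-out were constant over 50 weeks, retention at Week 10 would be S50^(10/50), where S50 is retention at Week 50:
- S50 = 0.30: 0.30^0.2 = 0.786, so 79% counted as completers against 30%
- S50 = 0.50: 0.50^0.2 = 0.871, so 87% against 50%
- S50 = 0.70: 0.70^0.2 = 0.931, so 93% against 70%

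The pattern of drop-out matters. With S50 = 0.50, the share counted could lie anywhere from 50% (all drop-out before Week 10) to 100% (all after).

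**6. The Visit 7 label.** Visits are named 1a, 1b, TV1 to TV14 and OV1 to OV4. The only one numbered 7 is TV7, the last in "Treatment Visits 3-7 (TV3-TV7, Treatment Period Weeks 5-21"), at Week 21. No patient has a first dose there. The primary window, Weeks 5 to 50, is 50 − 5 + 1 = 46 weeks. Under Section 19.9.2, which counts from the first dose, all 46 are covered.

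**The case against.** **Sections 11 and 12 define different things, so they may differ.** That is true in principle: treatment completion and study completion are separate concepts. But this study continues past the end of treatment, so study completion cannot sensibly come 40 weeks before treatment completion. Section 12 also contradicts itself, whatever Section 11 says.

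**Late drop-outs would remain visible.** This stands in part. The withdrawal date and reason go on the CRF, reasons for discontinuation are summarized (Section 19.4), and stops for lack of efficacy or adverse events are shown separately (Section 19.8.2). The information is not lost; the completion count is what would be wrong.

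**The percentages are conjecture.** They are, and are labelled so. Section 9.3 says that treatment-limiting gastrointestinal effects occur early. If early drop-out dominates, constant drop-out overstates retention at Week 10, and the gap is smaller than shown.

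**Stronger readings of Section 17.5.1.** A reader might infer that the primary-endpoint event set is wrong, because reading Visit 7 as TV7 would leave out Weeks 5 to 20, or 16 of 46 weeks (34.8%). The documents do not support this. The sentence is anchored on the first administration of study drug, which never occurs at TV7. Section 19.9.2, the analysis section, counts from the first dose. Section 17.5 records adverse events from consent, so none go uncollected. Counting 20 of 50 treatment weeks as lost would also use the wrong window, since titration is outside Weeks 5 to 50 by design. Nor does Section 17.5.1 omit worsening: it lists worsening of a pre-existing condition among the things an adverse event may be.

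**The text is superseded.** Version 2.0 is in the same file, but its text stops at heading 10.2. Whether either error survives there cannot be established. Its biopsy text (Sections 9.7.7.8.1 and 9.7.7.8.2) still refers to an Evaluation visit, so the check is worth making.

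**Conclusion.** The completer rule in Version 1.0 Section 12 is wrong for this study. It names a visit that is not scheduled, conflicts with Section 11 and with its own section, and has no correct counterpart in the supplied text. Read literally, it makes a completer of a direct entrant with 80% of planned treatment outstanding, and the disposition summary would then overstate completion. By how much depends on the timing of drop-out, which the documents do not give. The finding rests on the Version 1.0 schedule and on a literal reading of Section 12.

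The Visit 7 label is a contradiction to correct. It does not by itself alter the primary-endpoint event set.

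**What to change.** 1. **Section 12.** Define study completion as completing TV14 and the Washout and Safety Follow-up Visit. This works for direct entrants and for those coming from the Observation Period, since TV14 is the final treatment visit for both.
2. **Disposition.** Report study completion separately from treatment completion as defined in Section 11. This matters more under Version 2.0, where TV14 becomes an end-of-treatment visit that is also performed when a patient stops drug early. There, attendance at TV14 and the washout visit alone would not show that the planned treatment was completed.
3. **Section 17.5.1.** Replace the evening of Visit 7 with the evening of Visit 1a or 1b, so that it agrees with Sections 9.6.1, 9.6.5.3 and 19.9.2.
4. **Version 2.0.** Check Sections 12 and 17.5.1 for both errors and correct them there if they persist.

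The cost is one sentence in Section 12, a few words in Section 17.5.1, and matching wording in the CRF guidance and the SAP. No visit, procedure or data item changes. The reported completion rate may be lower than under a literal reading of the present rule.
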